Sample B:

Next, the study staff will say, “The little red circle (point to response option 2) should come next in order (point across stimulus from left to right, then point to question mark).”

Sample C:

Finally, the study staff will say, “This piece (point to response option 3) finishes the picture (point to question mark).”

3. Once the participant has completed the third sample question and before clicking the forward arrow, say the following:

“Now you know what to do. There are more pictures with missing pieces. Click the piece that finishes the picture. When the arrow turns blue, click it to see the next picture.”

Begin 20-minute Timer.

If the participant is not finished within 20 minutes, kindly ask the participant to close the window. (Do not click forward through the arrows)

Once the window is closed, the Raven’s Assessment is complete.

Computer-based surveys. The study staff will have the participants seated in the 302D office to complete the survey. The research staff will turn off the ring light and microphone, then accommodate the monitor, keyboard, and mouse in front of the participant, so the surveys can be completed in a comfortable position. The research staff will send a RC invitation to the participant by email beforehand, 1 day before the baseline visits occur. The study staff will kindly ask the participant to log into the email they initially gave during their screening call. After the participant has access to their email, ask the participant to find the email called “Post Visit” Make sure the participant has the correct email in place. After the participant has access to the Redcap surveys, select the participant’s preferred language on the Redcap platform.

The surveys the participant will complete are a physical activity survey, beverage intake survey, P50 CDC form, and residential history.

CGM Satisfaction Survey. The last survey that will prompt out is a satisfaction survey. The survey's purpose is to obtain a specific review from each participant about their entire study participation. The survey form will be captured on the RC platform.

Dietary Interview Request Form. After completing all the post visit activities, the study staff will fill out the NDSR Interview Request Form provided by the SCCLH team, which is the following:

<https://forms.office.com/pages/responsepage.aspx?id=HVNizmW2rkqhdQq1FBwZ2ryFXCgLS5hMj4r325rFPwlUNkw1OE9VQzRRTEJJTjk3ME1MVjRDSkk0VyQIQCN0PWcu>

P50 NDSR Dietary Call

The P50 staff will conduct a separate NDSR telephone-based interview with the participant following the completion of the post-visit. This interview will involve dietary recording prompts based on standardized protocols developed by the USDA for use in National Surveys of food intake. [name] will hold a separate interview to conduct this 45-minute assessment, utilizing 2-dimensional food models to guide portion size estimates.

Compensation. Before the study staff initiates the compensation procedure, the staff will ask the participant to return the two worn sensors. The study staff will ensure that both sensors are provided inside of each designated Ziploc baggie. The participants who participate in the entire post-visit procedures will receive two \$100.00 gift cards as compensation for the completion of the Post Visit. Besides obtaining the Post Visit compensation, the participant will receive another \$100.00 in gift cards for replacing the first sensor, and an additional \$200 in gift cards to compensate the participant for their sensor wear for 20 continuous days. In total the participant will receive \$500 in a form of gift cards to complete their entire study compensation. Throughout the study, the research staff will obtain gift cards from vendors already affiliated to USC.

G1-Continuous Glucose Monitoring Gift Card Log

To track efficient detailed records of each purchased and delivered gift card, the research staff will create a gift card log on an excel spreadsheet. When issuing a gift card to a participant, the study staff will kindly ask the participant to sign the gift card log including details on the gift card number, name of gift-card vendor, date, time, and the participant's ID that the gift card was issued to. An example of the Gift Card Log is provided in the Appendix _J_.

3.13.3 Final Study/Early Discontinuation Evaluations.

Participants should be actively followed through all study visits until the final visit is important to note that if a study participant is discontinued from treatment, he/she should still be followed to the end of the study.

Evaluations for the final study/early discontinuation visit should be described in this section.

The Post visit will take place on days 21-30, 1 to 10 days after the second sensor has been removed. The procedures that will take place are measuring the participants height and weight, the participant will fill out a physical activity, beverage intake, residential history, and P50 questionnaire; they will participate in a narrative semi-structured in-depth interview, and complete the CGM satisfaction survey, and self-report habit index.

The day before the visit, the study staff will send the participant an email and a text message containing the address, parking instructions, instructions to bring a piece of paper with their email address and correct password written in it, and a Google map directions link. Additionally, they will provide a study staff's cell phone contact number in case of transportation issues on the day of the visit or for rescheduling purposes. Within 48 hours of the visit, the participants will be contacted by phone to confirm their attendance.

P50 dietary recall. The P50 staff will conduct a separate phone-based interview with the participant following the completion of the post-visit. This interview will involve dietary recording prompts based on standardized protocols developed by the USDA for use in National Surveys of food intake. [name] will hold a separate interview to conduct this 45-minute assessment, utilizing 2-dimensional food models to guide portion size estimates.

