question will appear on the screen, asking the user if they want to pair the transmitter to the smartphone, the study staff will then guide the participant to click on “Pair New”. Once the App has linked with the sensor, the app will show a sign saying that the sensor will warm up for 3 hours and that no glucose data will be shown until the sensor has completely warmed up. After the pairing has been successful, the study staff will ask the participant to go to the “settings” icon found in the upper right corner of the G6 App, and they will click on the “Alerts” section. After the alerts page prompts out, the study staff will turn off the “Low” alerts and will click on the “High” tab to place 140mg as the level of high glucose alerts. Explain to the participant that the G6 App cannot be closed, that way all collected data is not lost. The study staff will make the remark that the participant’s smartphone’s Bluetooth always must be on. After completely setting up the G6 App, the study staff will then ask the participant to open the Dexcom Clarity app and the app will ask the participant to login with their Dexcom username and password. After login into the Dexcom Clarity app, the study staff will guide the participant to go into the “profile” section of their app, after touching that section the app will prompt a page where it will show a section called “Manage Data Sharing,” the study staff will ask the participant to select that section and the app will then ask the participant to “Share your CGM data with your clinic” and the participant will be guided to touch the “Continue” tab. After selecting the “continue” tab, the app will ask the user to “Enter clinic code.” The clinic code that will be used for the G1-study is: g1studyusc. After entering the G1-study clinic code, the participants’ CGM data will appear on the Clarity platform after the sensor has warmed up.

After the study staff has made sure that the participant has linked their smartphone to the CGM sensor, the staff will then link the applied sensor to the G6 PRO receiver. To do so, the staff will grab the G6 PRO reader and click the “On/off” button. After the receiver has turned on, the receiver will ask the user to enter the 4-digit sensor code. The study staff will enter the 4-digit code found in the adhesive backings of the applied sensor applicator. Once the study staff has entered the code. The receiver will take about 5 minutes to link the sensor to the receiver.

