The study staff will then congratulate the participant for successfully applying the sensor and pairing the sensor to their smartphone. After words of encouragement have been given, the staff will then explain to the participant that they will complete daily videos in which they will answer questions that the study staff will send through a text message every day, within those videos they will sincerely share their experience with the Dexcom sensor. The study staff will explain that on the days they obtain “high glucose” alerts, they will create a video describing in what situation the participant was in when the alarm was received; they will describe what foods they ingested before obtaining the alarm as well.

The final step of this procedure involves explaining to participants the signs and symptoms they should report to the research staff regarding the sensor. These include swelling, redness, bruising or bleeding. Participants must notify the research staff if the transmitter falls off or if any errors occur within the app. The study staff will make the remark that the participant cannot remove the sensor unless it is instructed by the study staff. Additionally, participants should be reminded that the transmitter-sensor is effective for 10 consecutive days. Provide each participant with a yellow folder to store the used transmitters. Remind the participant they are to bring their transmitters with them on their return visit.

[figure not shown]
Before the participant puts his/her smartphone away, the study staff will ask the participant if they already have a Zoom App and Zoom account and explain that this app is needed for the sensor replacement video call. If the participant does not have a Zoom account, the study staff will help and guide the participant to download the Zoom app and with the creation of a Zoom account.

Instructions for G6-Pro placement and transmitter attachment

For additional information related to inserting the sensor, please see the Dexcom G6 Pro CGM System User Guide

1BL017544 Rev

1. After the sensor is inserted and the transmitter has been snapped into the sensor pod, open the G6 app and follow prompts to create a username and password. Log in to the app and follow the set-up

wizard. Refer to the unblinded CGM patient handout that is included in your box.

- a. The study staff will keep the adhesive backings of the applicator because this adhesive contains the 4-digit code that will be entered into the receiver/reader.

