****Special instruction:**

Turn off low alerts of 70 for prediabetes.

Set up high alert at 140 for prediabetes

Then be sure to turn off all alerts after you have started up - go to settings on G6 app home page and turn always sound to off.

2. In your box you will find an invitation to share your data. Follow the instructions on how to accept the invitation.
 - a. Download the Dexcom Clarity App into the participant's smartphone
 - b. Enter the G1-Study clinic code: G1Study. By doing so the system will automatically populate the participant's glucose data into the Clarity system.
3. In 10 days, your G6 Pro sensor session will end. The app will let you know when it has finished. Peel off the entire sensor with a transmitter (like peeling off a Band-Aid) and place in the zip-lock bag and then place in the envelope provided.

4. Return transmitter to research team.
5. Be sure to keep your phone within 20 feet to retain transmission and do not swipe close the app at any time as this will stop transmission of CGM data.

An example of the Dexcom Training Checklist is provided in the [Appendix_G_](#).

G6 Reader

The reader, also known as a receiver, is the device from the Dexcom G6 Pro kit that helps the user verify that the session has started. The reader will not show any real time CGM data. The manufacturers describe this device as a compatible data extraction tool, this will help the research staff to upload patient data to Dexcom Clarity. In a blinded study scenario, the reader will be the only device receiving the data from the Dexcom transmitter. After the application of the Dexcom sensor-transmitter, the study staff will turn on the reader and the reader will ask for the serial number associated with the transmitter. The serial number is on the box, one of the inserts and the bottom of the transmitter. When you turn on the Reader and select “Download Data”, the first thing it asks for is the transmitter serial number.

Each G6Pro box has an insert that comes with 2 stickers which are the serial number. One sticker will be placed into the patient chart. If you are doing it electronically. We will keep a study record of the serial number of the transmitters by participant ID as shown below.

Study ID	Transmitter_1	Transmitter_2
001	xxxx	xxxx

Daily videos recording

An email will be sent automatically one day after the participant signs the ICF. The email will contain a RC link in which the participant will be able to upload their daily videos.

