After the application of the sensor, the study staff will reiterate to the participant that as mentioned during the ICF process, the participant will create daily videos using their smartphones. The study staff will explain that the participant will create a video after obtaining a “high glucose” alert, in which they will describe what foods they ingested before receiving the alarm and they will describe in what situation they were in in the moment that they obtain the alert. The study staff will explain in addition, the participant will receive a daily text with 2 questions that the participant will answer on a video at the end of the day at approximately 6:00 p.m. The study staff will clarify that the purpose of the daily videos is to record their entire experience with the Dexcom sensor throughout the CGM wear phase. The study staff will

explain that every day at 6pm they will also receive an email containing a link with instructions on how to record themselves, and a section link where they will upload their daily videos.

Video Upload Practice

An email will be sent automatically after the participant signs the ICF. The email will contain a RC link in which the participant will be able to upload a practice video during the visit.

After providing a clear explanation, the study staff and the participant will create a practice video in which the staff will explain to the participant the importance of the lighting for the video, and that the participant's face should be clearly seen. The staff will inform the participant to make their videos in silent places, to eliminate other noises on their video's audio.

The study staff will kindly ask the participant to check their email to ensure that they have received an email titled "Video Upload." If the participant cannot locate the email, the study staff will help locate the email either in the participant's email inbox or in the spam folder. If the study staff is unable to locate the email, the study staff will check the email address that the participant provided during their screening call. After checking the correct email address, the study staff will immediately contact the study's statistician, so that the participant can receive the video upload link.

Compensation

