The study staff will provide \$100 gift card compensation to all participants attending the baseline interview and complete the protocols. Since this is the last procedure, the participant will be involved with for this visit, the study staff will provide an envelope to the participant. The envelope will be labeled with the name of the study, the research coordinator's name and contact number. In the envelope the participant will locate two Ziploc baggies, 1 for each worn sensor. Each baggie will be labeled as "sensor 1" and "sensor 2;" the baggie will also contain one of the stickers designated for each sensor (these stickers will be found within the Dexcom G6 Pro kit box). The study staff will explain to the participant that the bag labeled "Sensor 1" is for them to put in the sensor that has been recently applied on the 10th day and the bag labeled "Sensor 2" is designated for the 2nd sensor they will apply on their own once they have completed the 20 days (about 3 weeks) of the CGM phase.

Data entry

The study staff will ensure to transfer the baseline data collected from the participant's chart into the RC system on the same day as the baseline visit. This will ensure that the main data capture system remains up to date.

CGM Wear Phase

The CGM wear phase will span 20 consecutive days. Throughout this period, we will gather data from the participants on a weekly basis. The sensor will be replaced once on day 10. Each morning, participants will receive text prompts to log dietary behaviors that triggered high out-of-range alarms; these logs will be recorded directly in the app by the participant. During the Zoom-supported sensor replacement call, the staff will replace the sensor and inquire about any adverse events or serious adverse events related to the sensor. Additionally, study staff will conduct Zoom sessions with participants on the 10th day of wearing transmitters during the CGM phase.

Dietary logs

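### The sensor-placement instructions set a high-glucose alert and then say to turn all alerts off, in conflict with the visit narrative and with the alert-triggered videos and dietary logs

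*Protocol*

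**What the plan says.** Protocol section 3.13.2 describes the alert set-up twice.

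- **CGM application narrative.** Staff turn off the low alerts and use the high-alert tab "to place 140mg as the level of high glucose alerts". No step turns everything off.
- **Special instruction, under the placement and transmitter instructions.** Low alerts go off, then "Set up high alert at 140 for prediabetes". The next line is "Then be sure to turn off all alerts after you have started up", and the same sentence gives the action: "go to settings on G6 app home page and turn always sound to off".

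Other text makes the high alert a prompt for data collection.

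- In the CGM application narrative, on days with a high alert, "they will create a video describing in what situation the participant was in when the alarm was received".
- Under Daily videos recording, participants make a video after an alert, in which "they will describe what foods they ingested before receiving the alarm".
- Under CGM Wear Phase, each morning "participants will receive text prompts to log dietary behaviors that triggered high out-of-range alarms".
- Under Dietary logs, the 6 pm text asks for foods eaten just before a high alert, and videos are to follow an alert.
- The schedule of assessments (section 3.8 and Appendix F) ties the dietary log to an out-of-range chime.
- Question 9 of the post-visit interview (Appendix I) asks when the participant noticed high alarms.

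**The concern.** Section 3.13.2 says its instructions should be detailed enough for a new or substitute team member to run the visit. A person following the narrative and a person following the special instruction could leave participants' phones in different states. The list is also unclear about who acts, because it moves between staff wording and wording addressed to the wearer.

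Two things are at stake. First, the daily videos and interviews supply the raw material for the educational clips (Protocol section 2). The alert-prompted videos are the ones that tie a particular meal or situation to a particular excursion. Total video minutes is also the SAP's other pre-specified outcome (6.2). Second, SAP section 3 asks whether CGM with smartphone feedback improves glycemic control. Whether a 140 alert reaches the wearer is plausibly part of that feedback, so mixed settings would be an unrecorded difference in what participants experienced.

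**Working it through.** The plan gives no figure to reproduce. The check sets the texts side by side.

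**Step 1: the two set-up texts.** Both turn low alerts off and set the high alert at 140. Only the special instruction adds a line about all alerts. It therefore conflicts with the narrative and, taken literally, with its own preceding line.

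**Step 2: the two readings of that line.**

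1. *Literal (all alerts off).* The 140 alert just set never fires. The event videos, and the logs keyed to alarms, lose their trigger.
2. *Sound only (the action named in the sentence).* The documents do not say that this setting disables an alert, so one may still show on screen. The audible chime named in section 3.8 and Appendix F is then lost or uncertain.

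Each reading conflicts with some of the data-collection text. Only the first removes the trigger outright.

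**Step 3: what does and does not need the alert.**

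| Item | Needs the alert? | Where |
|---|---|---|
| Event video after a high alert | Yes, as its stated trigger | 3.13.2, CGM application; Daily videos recording |
| Dietary log or report | Partly: a text asks for it, but the alarm defines the episode | 3.13.2, CGM Wear Phase; Dietary logs |
| End-of-day video answering two texted questions | No | 3.13.2, Daily videos recording |
| Post-visit interview | No, though question 9 presupposes alarms | 3.13.2; Appendix I |
| Five-minute glucose readings | No | 3.13, Glycemic variability |
| Change in mean glucose, Phase A to Phase B | Data capture does not | SAP 6.1, 8.2 |
| Total video minutes | In part | SAP 6.2, 8.3 |

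**Step 4: could the setting be recovered afterwards?** The body-measures form (Appendix E) and the replacement-call form (Appendix Q), as shown, have no alert field. The replacement script (Appendix H) pairs a new transmitter without checking alert settings, and the documents do not say whether settings carry over. With 20 participants and two wear periods, 20 × 2 = 40 participant-periods have an alert status that the pages shown do not capture in a dedicated field. This is the number unrecorded, not the number set wrongly. The appendices also state that there is no deviation log for this study.

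**The case against.** The strongest case on the other side is that the sentence specifies only one action, a sound setting. Setting a 140 alert would be pointless if it were disabled at once, the narrative has no all-off step, and the interview expects alarms to have been noticed. Silencing is thus at least as plausible as disabling. In addition, texts solicit the dietary reports, participants can see readings every five minutes in the app, and no SAP endpoint counts alert-triggered events. The documents describe the feedback as the five-minute readings, so treating the alert as part of it is an inference. Several form appendices show only one page, and the replacement-call form has free text for app problems. Nothing shows that any phones were in fact set differently.

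Most of this stands, and it limits the point. A reader might infer that following the special instruction removes the triggering event, or that every alert-prompted video and log is lost. The documents support that only on the literal reading, and even then a wearer could notice a high value on screen. A reader might also infer that the primary outcome data are compromised, but they are captured automatically whatever the alert setting.

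The objection does not remove the contradiction. The sound-only reading still conflicts with the chime in the schedule of assessments, and nothing tells staff which reading applies.

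**Conclusion.** The contradiction is real and should be corrected. It is an inconsistency in operating instructions that bears on a stated data-collection step. It is not a flaw in the primary analysis.

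The likely effects are fewer alert-prompted videos and dietary logs, possibly lower total video minutes, and unrecorded variation in feedback between participants or between wear periods. None of these can be sized: the documents give neither the share of participants set up each way nor the expected number of alerts. The range is therefore none to all of the 20 participants.

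The conclusion assumes that the form pages shown are representative. The feedback part also assumes that an alert adds something to the on-screen readings, which the documents do not state.

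**What to change.** Reconcile the special instruction with the CGM application, Daily videos recording, CGM Wear Phase and Dietary logs text in section 3.13.2, and with the schedule of assessments in section 3.8 and Appendix F, so that one alert configuration is described everywhere. State explicitly whether alerts are disabled or only silenced. Record the alert status for each participant and wear period, for example with one field on the baseline form and one on the replacement-call form. Which configuration is right is for the study team to decide.

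The cost is a short text correction and those two fields. Timing limits what this can achieve. Section 3.6 puts the final screening at August 30, 2024, and section 3.17.4 describes visits in the past tense. If wear is already complete, new fields cannot recover past settings. The manual and the study report should then state which configuration was used, or that it is unknown, alongside the summary of video minutes.
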